11.2.2 Analysis of the Exploratory Endpoints

The analysis of exploratory endpoints assumes that we have $\leq 10\%$ of patients with at least one missing outcome value. A complete case analysis will be used as a preliminary approach to establish the “baseline” results prior to using a mixed model for repeated measures (MMRM) or multiple imputation to account for missing values.

Number of good days (weeks 1-4, 1-12, and 1-24)

The weekly difference in mean number of good days will be estimated using a MMRM. The model will include the following independent variables:

- Week as a factor (week 1, week 2, week 3, week 4...week n)
- Treatment indicator (eptinezumab vs other advanced therapies)
- Interaction of treatment and week (i.e., treatment*week 1...treatment*week 2...treatment*week n)
- A vector of covariates identified to be significantly different between treatment groups after randomization.

We will assume that residuals are normally distributed, and we will also assume an unstructured covariance structure of the residuals. The Kenward-Roger approximation will be used to estimate standard errors. The hypothesis tested will be that the interaction term of treatment and week is significantly different from zero using a two-sided test at $p < 0.05$. The

population level summary will be the difference in mean number of good days at weeks 1-4. The analysis will also be conducted for weeks 1-12 and 1-24. If the model fails to converge, then other covariance structures will be utilized.

EQ-5D score (weeks 1-4, 1-12, and 1-24)

The weekly difference in the EQ-5D score will be estimated using a MMRM. The model will include the following independent variables:

- Week as a factor (week 1, week 2, week 3, week 4...week n)
- Treatment indicator (eptinezumab vs other advanced therapies)
- Interaction of treatment and week (i.e., treatment*week 1...treatment*week 2...treatment*week n)
- A vector of covariates identified to be significantly different between treatment groups after randomization.

We will assume that residuals are normally distributed, and we will also assume an unstructured covariance structure of the residuals. The Kenward-Roger approximation will be used to estimate standard errors. The hypothesis tested will be that the interaction term of treatment and week is significantly different from zero using a two-sided test at $p<0.05$. The population level summary will be the difference in mean EQ-5D score at weeks 1-4. The analysis will also be conducted for weeks 1-12 and 1-24. If the model fails to converge, then other covariance structures will be utilized.

HCRU (weeks 1-4, 1-12, and 1-24)

The difference in cumulative mean HCRU will be estimated using a negative binomial model. The analysis will be stratified by type of HCRU (i.e., outpatient, inpatient hospitalization, emergency department/urgent care visits, and migraine-specific medications such as triptans). Independent variables will include a treatment indicator (eptinezumab vs other advanced therapies) and a vector of covariates identified to be significantly different between treatment groups after randomization. The hypothesis tested will be that the treatment term is significantly different from zero using a two-sided test at $p<0.05$. The population level summary will be the relative difference in mean HCRU at weeks 1-4. The analysis will also be conducted for weeks 1-12 and 1-24. If there are a substantial number of observations with a value of zero HCRU, then a zero-inflated negative binomial model will be explored.

HIT-6 change from baseline score (month 1, 3, and 6)

The mean HIT-6 change from baseline score will be estimated using a mixed model for repeated measures (MMRM). The model will include the following independent variables:

- Month as a factor (Baseline month 0, month 1, month 3, and month n)
- Treatment indicator (eptinezumab vs other advanced therapies)
- Interaction of treatment and month (treatment*baseline...treatment*month 1...treatment*month n)

- A vector of covariates identified to be significantly different between treatment groups after randomization.

We will assume that residuals are normally distributed, and we will also assume an unstructured covariance structure of the residuals. The Kenward-Roger approximation will be used to estimate standard errors. The hypothesis tested will be that the interaction term of treatment and month is significantly different from zero using a two-sided test at $p<0.05$. The population level summary will be the difference in mean HIT-6 change from baseline score at month 1, month 3, and month 6. If the model fails to converge, then other covariance structures will be utilized.

MIDAS change from baseline score (month 3 and 6)

The mean MIDAS change from baseline score will be estimated using a MMRM. The model will include the following independent variables:

- Month as a factor (Baseline month 0, month 3 and month n)
- Treatment indicator (eptinezumab vs other advanced therapies)
- Interaction of treatment and month (treatment*baseline, treatment*month 3, treatment*month n)
- A vector of covariates identified to be significantly different between treatment groups after randomization.

We will assume that residuals are normally distributed, and we will also assume an unstructured covariance structure of the residuals. The Kenward-Roger approximation will be used to estimate standard errors. The hypothesis tested will be that the interaction term of treatment and month is significantly different from zero using a two-sided test at $p<0.05$. The population level summary will be the difference in mean MIDAS change from baseline score at month 3 and month 6. If the model fails to converge, then other covariance structures will be utilized.

PI-MBS (weeks 1-4, 1-12, and 1-24)

Among daily headache reports, the weekly proportion of each most bothersome symptom (e.g., pain worsened by physical activity, throbbing head pain, nausea, vomiting, photophobia, phonophobia, difficulty concentrating, visual aura, other aura, or other) associated with a headache and proportions of reports with no headache will be calculated for the eptinezumab and advanced migraine therapy group. The average weekly severity associated with each most bothersome symptom will be calculated. The trend in the weekly proportion and severity of each most bothersome symptom will be descriptively compared between the eptinezumab and advanced migraine therapy group.

TSQM score (week 24)

The difference in mean TSQM score for each domain (effectiveness, side effects, convenience, and overall satisfaction) at week 24 will be estimated using an ordinary least

square model. Independent variables will include a treatment indicator (eptinezumab vs other advanced therapies) and a vector of covariates identified to be significantly different between treatment groups after randomization. The hypothesis tested will be that the treatment term is significantly different from zero using a two-sided test at $p<0.05$. The population level summary will be the difference in mean TSQM score at week 24.

Index drug switching (weeks 1-12, and 1-24)

The difference in the odds of index drug switching will be estimated using a logistic regression model. Independent variables will include a treatment indicator (eptinezumab vs other advanced therapies) and a vector of covariates identified to be significantly different between treatment groups after randomization. The hypothesis tested will be that the treatment term is significantly different from zero using a two-sided test at $p<0.05$. The population level summary will be the odds ratio of index drug switching in the eptinezumab group relative to other advanced therapies. The analysis will be conducted weeks 12 and 24.

SDMQ-9 (screening and week 24)

The average SDMQ-9 score will be calculated for each treatment group and descriptively compared at screening and week 24.

SURE score at screening

The average SURE score will be calculated for each treatment group and descriptively compared at screening.

PAM-10 score (screening, week 12 and 24)

The average PAM-10 score will be calculated for each treatment group and descriptively compared at screening, week 12, and week 24.

ISS score (screening, week 12 and 24)

The ISS score or item responses will be analyzed descriptively using averages and proportions in the eptinezumab group at screening, week 12, and week 24.

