11.2 Analysis Methodology for the Exploratory Endpoints

11.2.1 Estimand for the Number of Good Days (Week 1-4, 1-12, and 1-24) and Exploratory Endpoints

A summary of the intercurrent events that will be addressed and the estimand attributes can be found below.

The estimand is the difference in the mean weekly number of good days within each specified time interval between eptinezumab compared to other advanced preventive therapies (erenumab, fremanezumab, galcanezumab, or onabotulinumtoxinA) in adults with migraine on concomitant acute migraine therapy who have failed ≥ 2 prior oral preventive therapies and who are naïve to advanced migraine therapy based on a treatment policy strategy in which patients are analyzed according to the randomized group and are included in the analysis regardless of discontinuation or switching of the index migraine therapy during the follow-up period.

Intercurrent events that will be addressed include:

- Discontinuing the index preventive migraine medication with or without initiation of a new preventive therapy (i.e., a treatment switch).
- Withdrawal from the study due to lack of efficacy, adverse event, participant request, physician request, or loss to follow-up.
- Interruption or termination of infusions.

Attributes of the estimand for the number of good days include:

- The index treatment of interest is eptinezumab (100 mg or 300 mg) compared to other advanced preventive therapies (erenumab 70 mg or 140 mg, fremanezumab 225 mg or 675 mg, galcanezumab 120 mg, and onabotulinumtoxinA 155 units)
- The population is all patients with migraine who fulfil the inclusion and exclusion criteria.
- The primary endpoint of interest is the mean number of good days across weeks 1-12 after randomization
- The population-level summary is the mean difference between eptinezumab and other advanced preventive therapies for the endpoint

Estimands for the remaining exploratory endpoints can be formulated similarly to the estimand for the number of good days described above.

EQ-5D (weeks 1-4, 1-12, and 1-24)

- The endpoint to be obtained is the weekly EQ-5D score in each specified time interval
- The population level summary is the difference in mean weekly EQ-5D score in patients on eptinezumab relative to advanced migraine therapies in each time interval

PI-MBS (weeks 1-4, 1-12, and 1-24)

- The endpoint to be obtained is the weekly most bothersome symptom and associated severity

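### For good days and EQ-5D the SAP tests treatment-by-week, but its estimand is the interval-mean difference, so the p-value answers a different question

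*SAP*

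**What the plan says.** SAP 11.2.1 states for good days: "The estimand is the difference in the mean weekly number of good days within each specified time interval". The intervals are weeks 1-4, 1-12 and 1-24, and good days over weeks 1-12 is singled out as the endpoint of main interest. The summary measure is set out as follows: "The population-level summary is the mean difference between eptinezumab and other advanced preventive therapies for the endpoint". EQ-5D has the same form: "The population level summary is the difference in mean weekly EQ-5D score in patients on eptinezumab relative to advanced migraine therapies".

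SAP 11.2.2 fits a mixed model for repeated measures to each endpoint. The terms are week as a factor starting at week 1 (no baseline level), a separate treatment indicator, the interaction, and covariates found to be imbalanced. The interaction is listed as "Interaction of treatment and week (i.e., treatment*week 1...treatment*week 2...treatment*week n". The hypothesis sentence is the same for both endpoints: "The hypothesis tested will be that the interaction term of treatment and week is significantly different from zero using a two-sided test", at the 0.05 level.

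The reported summary is again the interval mean: "population level summary will be the difference in mean number of good days at weeks 1-4" for good days and "The population level summary will be the difference in mean EQ-5D score at weeks 1-4" for EQ-5D, repeated for the two longer intervals. No contrast, weighting, confidence interval or test is attached to it.

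For HCRU, TSQM and drug switching, the same section tests the treatment term itself. The multiple-imputation sensitivity analysis in SAP 11.2.6 also tests a treatment term for good days and EQ-5D, without saying whether the interaction is in that model.

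**The concern.** In a model with a treatment main effect and weeks from 1 onward, the interaction null is that all weekly treatment differences are equal. The estimand's null is that their average is zero. Neither implies the other.

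The p-value would therefore be printed beside an interval-mean difference that it does not test, including for good days over weeks 1-12. A steady advantage of any size would be no more likely to be called significant than no advantage. An early benefit cancelled by later harm could be called significant. SAP 2.2 frames the key question as whether eptinezumab improves on the basket of available treatments, which is a question about level and not about change between weeks.

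HIT-6 and MIDAS carry the same hypothesis sentence but are not part of this point. Their time factor includes baseline, so the interaction there can carry change from baseline.

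**Working it through.** **Inputs.** From the SAP: 100 per arm (15.1), two-sided 0.05, unstructured covariance, K = 4, 12 or 24 weeks. The 3:2:1 allocation in chronic migraine is 1:1 once the comparators are pooled. The SAP gives no effect size for these endpoints, so 0.36 and 0.23 are borrowed from Panel 6. They are migraine-day effects against placebo, whereas this trial compares active drugs. Assumed: complete data, equal weekly variances, and correlation either compound symmetric (CS) at 0.3, 0.5 or 0.7, or AR(1) at 0.8.

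**Plan's own figure.** For an effect s on the interval mean, noncentrality = s × √(n/2) = 0.36 × √50 = 2.546 on 198 df. Power is 72%, as in Panel 6. For 0.23 it is 0.23 × √50 = 1.626, or 37%, also as in Panel 6.

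**Weekly effect.** A constant weekly effect giving interval-level effect s is s × √(mean element of the correlation matrix R). For K = 12 and CS 0.5 this mean is (1 + 11 × 0.5)/12 = 0.542, so the weekly effect is 0.36 × √0.542 = 0.265. Over all settings it runs from 0.20 to 0.32.

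The SAP does not say how the interaction is to be tested, so three readings were checked.

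**Reading 1: joint test of the K−1 contrasts against week 1.** Hotelling T², λ = (n/2) δ′V⁻¹δ, where δ holds the differences from week 1 and V is their covariance matrix; df are (K−1, 2n−K). With a constant benefit δ = 0, so λ = 0 and rejection is 5% whatever the benefit. Simulation gave 4.6-5.4% at weekly effects of 0, 0.36 and 1.0.

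**Reading 2: each coefficient against week 1, unadjusted.** The chance of at least one rejection is inflated, but a constant benefit still cancels out of every coefficient.

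**Reading 3: all K weekly differences tested jointly.** λ = (n/2) d′R⁻¹d, where d holds the weekly differences; df are (K, 2n−K−1). Under CS with a constant benefit this reduces to 50 × 0.36² = 6.48 for every K. The same signal is spread over more degrees of freedom as K grows.

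Constant benefit, interval-level effect 0.36 (range over the four correlation structures):

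| Test | 4 weeks | 12 weeks | 24 weeks |
|---|---|---|---|
| Interval mean | 72% | 72% | 72% |
| Reading 1 | 5% | 5% | 5% |
| Reading 2, at least one rejection (about the same with no effect) | 11-13% | 23-31% | 34-46% |
| Reading 3 | 49-51% | 30-33% | 21-23% |

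If 0.36 applies to each single week instead, the interval mean has 82% to over 99% power and reading 1 stays at 5%.

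**Reversal with zero mean.** The weekly effect runs linearly from +0.36 to −0.36. Under CS, λ = (n/2) Σ(dᵢ − d̄)²/(1 − ρ). For K = 12, Σdᵢ² = 0.36² × 572/121 = 0.613, so at ρ = 0.5, λ = 50 × 0.613/0.5 = 61.3 and rejection exceeds 99%. Over all settings reading 1 rejects 51-100% of the time; the interval-mean test rejects 5%.

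**Fading benefit.** The effect falls linearly to zero, with interval-level effect 0.36. Reading 1 has 74-100%, 35-100% and 15-100% power at 4, 12 and 24 weeks, against 72% for the interval mean.

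**Sensitivity analysis (11.2.6), constant interval-level effect 0.36.** If the model has no interaction, the treatment term is a common effect with 72-75% power. If the interaction is present under reference coding, the term is one week's difference, with 29-61%.

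**The case against.** The strongest reply is that the wording need not mean the joint test. SAP 11.2.2 opens by saying that the weekly difference will be estimated, lists an interaction term for every week, and speaks of a two-sided test. That could mean a separate test of each week's treatment difference, which does see a constant benefit. At interval-level 0.36, simulation gives at least one significant week in roughly 80%, 90% and 91-95% of trials at 4, 12 and 24 weeks. With no effect, however, it also gives at least one in roughly 12-17%, 24-40% and 31-60%. So blindness to a constant benefit does depend on the reading, but this reading also fails to test the interval mean and adds uncontrolled multiplicity.

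Reading 3 also has some support. It makes the separate treatment indicator redundant, but the SAP lists every factor level elsewhere too, so that is weak evidence against it. It remains an omnibus test and does not test the mean.

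SAP 11.2.6 does pair a treatment-term test with the difference in means over each interval. That is partial mitigation only: it is a sensitivity analysis, and what its treatment term means depends on coding that is not stated.

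Protocol 3.3 makes all objectives exploratory, and the model can estimate the interval mean, which is reported. This limits the consequence. Durability is a stated interest in SAP 2.2, and for a fading effect the interaction can be the more powerful test. That justifies keeping it as a secondary analysis, but durability is not the estimand in 11.2.1.

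**Conclusion.** The point holds. For good days and EQ-5D the hypothesis named in the main analysis is not a hypothesis about the stated estimand, and no plausible reading of the sentence makes it one. Under the ordinary joint test, rejection is 5% for any constant benefit. That result follows from the algebra and does not depend on an assumed effect, SD or correlation.

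The other sizes (72% against 5%, and 51-100% rejection at zero mean difference) are illustrations. They rest on borrowed placebo-controlled migraine-day effects, assumed correlations, complete data and equal weekly variances; good days is in fact bounded at 0 to 7.

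The fault is confined to the named test and its p-value. The model and the reported mean difference are sound on this point. It should be fixed, but it does not threaten the trial.

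**What to change.** In SAP 11.2.2, for good days and EQ-5D, name as the tested hypothesis the treatment contrast averaged with equal weights over weeks 1-4, 1-12 and 1-24. Report it as an LS-mean difference with a 95% confidence interval from the model already specified. Use the same contrast in 11.2.6, and state whether treatment-by-week is in that model. Keep treatment-by-week as a secondary description of durability, identified as a joint test.

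The cost is SAP wording and a different contrast statement in the program. Data collection, sample size and participants are unaffected.

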11.2.3 Strategies for Addressing Intercurrent Events in the Exploratory Estimands

The goal of this pragmatic trial is to measure the effectiveness of migraine preventive treatments in “real-world” conditions regardless of the occurrence of intercurrent events during the follow-up period. Therefore, all intercurrent events will be addressed using a treatment policy strategy, in which all patients will be analysed despite the occurrence of an intercurrent event. This strategy reflects the intent-to-treat principle in which patients are analyzed regardless of protocol deviations.

Use of acute medication to treat a migraine headache

A treatment policy strategy will be used to address acute medication usage during the follow-up period. Patients with available endpoint data will be analysed regardless of acute medication use during the follow-up period.

Discontinuing the preventive migraine medication with or without initiation of a new preventive therapy.

A treatment policy strategy will be used to address patients who switch or discontinue the index therapy. Patients with available endpoint data will be analysed according to their index therapy regardless of switch or discontinuing the index therapy.

Withdrawal from the study due to lack of efficacy, adverse event, participant request, physician request, or loss to follow-up.

A treatment policy strategy will be used to address patients who withdraw from the study for any reason. Imputation of missing data will aim to ensure that all observations with missing outcome values can be used in the analysis.

Interruption or termination of infusions.

A treatment policy strategy will be used to address patients who experience an interruption or termination of infusions. Patients with available endpoint data will be analysed regardless of infusion interruption or termination.

11.2.4 Rationale for Selected Analysis for the Exploratory Endpoints

The number of good days, EQ-5D score, HIT-6, and MIDAS are continuous longitudinal data (i.e., correlated observations across time on the same individual) that are approximately normally distributed. Therefore, a MMRM is optimal for these outcomes. HCRU are counts, which follows a right skewed distribution and values are restricted >0 , therefore, a negative binomial model is appropriate. The TSQM is approximately normally distributed and ordinary least squares is appropriate. Index drug switching is a binary outcome measure, and a logistic regression is appropriate. Other patient reported outcomes such as the PI-MBS, SDMQ-9, SURE, PAM-10, and ISS are discrete or categorical variables and describing the endpoints by proportion, mean, or median is appropriate.

11.2.5 Evaluation of Model Assumptions for the Analysis of Exploratory Endpoints

The assumption of normality of the patient-reported outcomes will be evaluated by visual inspection of the distribution of the outcomes, residual Q-Q plots, and scatter plot of standardized residuals vs predicted values.

11.2.6 Sensitivity Analyses of the Exploratory Endpoints

Number of good days (weeks 1-4, 1-12, and 1-24), EQ-5D score (weeks 1-4, 1-12, and 1-24), HIT-6 change from baseline score (month 1, 3, and 6), and MIDAS change from baseline score (month 3 and 6)

To test the robustness of the results with respect to missing data, the missing data will be imputed using multiple imputation by chained equation assuming data is missing at random.¹ First, the proportion and pattern of missing outcome values will be evaluated, and descriptive statistics of variables with missing values will also be evaluated. Additionally, among outcome variables with missing data, the association of missingness with other variables will be measured. Missing values will be imputed using fully conditional specification imputation in which each variable with missing values is imputed using regression (type of regression dependent on the variable distribution). Imputation models will be specified to include all analytic variables and additional variables that are associated with missingness. A minimum of 20 imputed datasets will be generated.² Trace plots for continuous variables and tabulations for categorical variables of the imputed datasets will be evaluated to assess the validity of imputations methods. Methods to “penalize” missing values will also be explored. Only observations in the eptinezumab group will be used to impute missing data in patients randomized to eptinezumab, and only observations in the comparator arm will be used to impute missing data in patients randomized to the comparator arm.

A mixed model with repeated measures (MMRM) will be used to evaluate the association between treatment and patient reported outcomes and a generalized linear model (log link and gamma distribution) will be used to evaluate the association between treatment and HCRU across the imputed datasets. Coefficients and standard errors obtained from each imputed dataset will be pooled and combined for inference using PROC MIANALYZE in which regression coefficients are averaged across imputations and standard errors are estimated to incorporate uncertainty within imputations and between imputations.¹ The hypothesis tested will be that the treatment term is significantly different from zero using a two-sided test at $p<0.05$. The population level summary will be the difference in means at each specified time interval.

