18.6 HCRU (weeks 1-4, 1-12, and 1-24)

All-cause medical HCRU will include outpatient physician visits, inpatient hospitalizations, urgent care visits, and emergency department visits. Medications (over-the-counter and

prescription) used for the acute relief and prevention of migraine will also be included. HCRU is reported by patients using the ePRO application on a daily basis and on the HCRU follow-up questionnaire, which is a comprehensive review of patient HCRU obtained by study coordinators during the monthly visits. Since the HCRU follow-up questionnaire contains more comprehensive information (i.e., patient reported HCRU and any that may not have been reported by the patient on the ePRO), the analysis will be based on the HCRU follow-up questionnaire. However, data reported in the ePRO and follow-up questionnaire will be compared to assess for inconsistencies. Missing values will not be imputed.

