18.6.1 Medical HCRU

Medical HCRU will be ascertained based on the HCRU follow-up questionnaire. Reported counts of HCRU will be summed across weeks 1-4, 1-12, and 1-24 based on the date of reported healthcare utilization.

Reported HCRU will be stratified as outpatient (physician office visit, outpatient service use, outpatient surgery), urgent care visit, emergency room visit, and inpatient service.

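### The HCRU sensitivity model in SAP 11.2.6 is a gamma GLM that cannot take zero counts, and the SAP is inconsistent on whether HCRU is imputed

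*SAP*

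**What the plan says.** **Main model (SAP 11.2.2).** "The difference in cumulative mean HCRU will be estimated using a negative binomial model". "The analysis will be stratified by type of HCRU": outpatient, inpatient, emergency department/urgent care, and migraine-specific medications. Zeros are provided for: "If there are a substantial number of observations with a value of zero HCRU, then a zero-inflated negative binomial model will be explored". The result is reported as a relative difference in means.

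**Endpoint (SAP 18.6.1).** "Reported counts of HCRU will be summed across weeks 1-4, 1-12, and 1-24".

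**Stated range (SAP 11.2.4).** "HCRU are counts, which follows a right skewed distribution and values are restricted >0". The same sentence then concludes that a negative binomial model is suitable.

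**Sensitivity model (SAP 11.2.6).** After describing multiple imputation, the section says that "a generalized linear model (log link and gamma distribution) will be used to evaluate the association between treatment and HCRU across the imputed datasets". It has no rule for zeros, gives no reason for leaving the negative binomial, and reports a difference in means. The endpoints listed at the head of the section are good days, EQ-5D, HIT-6 and MIDAS; HCRU is not among them.

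**Imputation (SAP 18.6 and 11.2.3).** For HCRU, 18.6 says "Missing values will not be imputed". Section 11.2.3, on withdrawal, says in general terms that imputation should allow every observation with a missing outcome to be used.

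**The concern.** The plan names a distribution for strictly positive data and applies it to counts that can be zero. An analyst who follows 11.2.6 will either get no fit or have to find a way round the zeros. Dropping them restricts the analysis to participants with some use. Use is itself an outcome after randomisation, so the two groups left are no longer those that randomisation created, and the analysis departs from the as-randomised, treatment-policy approach of SAP 11.1 and 11.2.3. Any other workaround, such as adding a constant or using a quasi-likelihood, would be chosen after the data are seen.

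HCRU is a listed between-group objective (Protocol section 2, item 4), and helping payers to understand economic cost is a stated purpose (Protocol 3.3). A robustness check on this endpoint that fails, or that appears to contradict a real effect, weakens that use. The imputation text adds a second problem: a programmer cannot follow 11.2.3, 11.2.6 and 18.6 together.

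**Working it through.** **Inputs.** From the SAP: summed counts (18.6.1), negative binomial main model (11.2.2), log-link gamma sensitivity model (11.2.6), two-sided 0.05 test, 100 per arm (section 15.1). The documents give no HCRU rate, zero share, effect size or power, so there is no plan figure to reproduce. Every rate below is an assumption.

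**Step 1: zeros and the gamma model.** A summed count of visits or admissions is zero for anyone with none in the window. The gamma deviance contains log(y), which is undefined at y = 0. As a trial, a log-link gamma GLM was run in R 4.3.3 on simulated counts of which 69% were zero. It stopped with an error saying that non-positive values are not allowed; it did not drop to users only. SAS, the other package named in SAP section 16, was not tested.

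**Step 2: what is estimated if zeros are dropped.** For mean m, the mean among users is E[Y | Y>0] = m / (1 − P0), where P0 is the zero probability.

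Poisson, P0 = exp(−m), true ratio 0.50:

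| Means (control v eptinezumab) | Mean among users | Users-only ratio | Share of log ratio kept |
|---|---|---|---|
| 0.2 v 0.1 | 1.103 v 1.051 | 0.95 | 7% |
| 0.5 v 0.25 | 1.271 v 1.130 | 0.89 | 17% |
| 1 v 0.5 | 1.582 v 1.271 | 0.80 | 32% |
| 5 v 2.5 | 5.034 v 2.724 | 0.54 | 89% |

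In the first row, exp(−0.2) = 82% of controls and exp(−0.1) = 90% of eptinezumab participants have zero use. The share kept is log(users-only ratio) / log(0.50), for example log(0.952) / log(0.50) = 0.07.

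Negative binomial with dispersion k, P0 = (1 + km)^(−1/k). For k = 1 the mean among users is 1 + m, so a true ratio of 0.50 gives (1 + m/2) / (1 + m): 0.83 at m = 0.5, 0.75 at 1, 0.58 at 5, 0.55 at 10.

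Share of the log ratio kept over k = 0, 1, 2 and true ratios 0.7 and 0.5:

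| Control mean | 0.1 | 0.3 | 0.5 | 1 | 2 | 5 | 10 |
|---|---|---|---|---|---|---|---|
| Share kept | 4-11% | 10-26% | 17-36% | 32-51% | 55-64% | 76-93% | 84-100% |

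**Step 3: effect on power.** Simulation with 100 per arm, k = 1, true ratio 0.50 and about 600 runs per setting. The negative binomial used all counts, with dispersion fixed at its true value; the gamma model used non-zero counts only.

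| Control mean | Gamma ratio, users only | Gamma power | Negative binomial power |
|---|---|---|---|
| 0.3 | 0.89 | 12% | 50% |
| 0.5 | 0.85 | 22% | 67% |
| 1 | 0.75 | 56% | 89% |
| 2 | 0.66 | 83% | 96% |
| 5 | 0.58 | 97% | 99% |

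The negative binomial estimate was 0.49-0.50 throughout. With no true effect (mean 1, k = 1) the users-only gamma test rejected in 4.3% of runs, so in that setting the damage is attenuation and lost power, not false positives.

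**Step 4: the imputation text.** The imputed datasets of 11.2.6 cover the four listed endpoints. Under 18.6 the HCRU values in them stay as observed. If the covariates in the HCRU model are complete, each dataset then gives the same HCRU estimate, and pooling returns the single-dataset result. That says nothing about missing HCRU, although robustness to missing data is the stated purpose of 11.2.6. Under 11.2.3, read generally, HCRU would be imputed and 18.6 would be wrong.

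**The case against.** Much can be said for the plan. The main HCRU analysis uses a suitable model and allows for zeros. The wrong range in 11.2.4 does no harm there, because the same sentence settles on a negative binomial. This is a sensitivity analysis of one exploratory endpoint in a study with no primary objective (Protocol 3.3), and no decision rule depends on it. HCRU is missing from the endpoint list of 11.2.6, which suggests a stray clause. All of that stands, and it limits the importance of the point.

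A reader might also infer more than the text supports:

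- **That the analysis would be of users only.** This is one of two outcomes. In R the model stops with a visible error and gives no misleading estimate.
- **That a true effect would be largely erased.** This depends on rates that the documents do not give. It is plausible for admissions, for emergency or urgent care, or for weeks 1-4. It need not hold for outpatient contacts or medication counts over 24 weeks, where means may be high.
- **That the imputed datasets will not exist.** They will, for the patient-reported outcomes. Only HCRU values are left unimputed.
- **That the SAP expects many zeros.** Its fallback is conditional; it allows for zeros and does not predict their share.

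None of this rescues the gamma model, which remains invalid for any stratum and window with even one zero.

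**Conclusion.** The point holds as a specification error in the HCRU sensitivity analysis. The gamma GLM cannot fit the endpoint as defined: it will fail or, if zeros are removed, give a non-randomised comparison of users that is biased towards no difference. The bias is severe where use is rare (at control means of 0.5 or less, 4-36% of the log effect is kept) and much smaller where use is frequent (76-100% kept at means of 5 and 10). These figures rest on assumed Poisson or negative binomial counts with dispersion 0 to 2 and true ratios of 0.7 and 0.5. The model's failure on zeros needs no such assumption.

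Separately, 11.2.3, 11.2.6 and 18.6 disagree on whether HCRU is imputed, and 11.2.6 reports a difference in means where 11.2.2 reports a relative one. The documents do not support any conclusion that the main HCRU result is compromised.

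**What to change.** 1. **SAP 11.2.6:** replace the gamma GLM. Any HCRU model kept there should be the negative binomial of 11.2.2, zero-inflated on the same condition, on all full-analysis-set participants as randomised, with the same relative summary. Check the HCRU summary in 11.2.1, which speaks of a difference in means, against it.
2. **SAP 11.2.4:** change the stated range from above zero to zero or above.
3. **HCRU imputation:** reconcile 11.2.3, 11.2.6 and 18.6. The simplest course is to take HCRU out of the imputed-data analysis, leave 18.6 as it is, and note the exception in 11.2.3. HCRU then has no imputation-based check. If a check on withdrawals is wanted without imputation, the negative binomial with log follow-up time as an offset would serve.

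The alternative is to impute HCRU. Section 18.6 would then have to change, HCRU would join the list at the head of 11.2.6, and an imputation model for counts would be needed.

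The simple course costs only SAP wording and needs no new data. The alternative adds specification and programming work.
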